5.2.1 Citrulline Arm

Patients randomized to citrulline will receive an initial intravenous bolus of 20 mg/kg (to a maximum of 1500 mg) L-citrulline over 10 minutes. The study solution will be prepared as a 5% isotonic solution (50 mg/mL) in 5% dextrose water. Immediately after the initial bolus, a continuous intravenous infusion of L-citrulline at 9 mg/kg (max 700 mg) per hour will be administered through a dedicated intravenous line or port of a multi-lumen catheter.

5.2.2 Placebo Arm

Patients randomized to placebo arm will receive an infusion of 5% dextrose water matched for volume and color to the citrulline infusion. The placebo infusion will consist of an initial iv bolus (up to 30 mL) over 10 minutes followed by a continuous infusion of 5% dextrose water (about 15 mL/hr). The initial bolus and subsequent infusion will be administered through a dedicated intravenous line or port of a multi-lumen catheter.

5.2.3 Drug Interruptions

Interruptions of study infusions should be avoided. As the study drug poses no known risk during procedures, infusions should be continued during bedside procedures. If the study infusion must be interrupted, it should be restarted at the same infusion rate as soon as possible. In cases where the infusion was interrupted, the infusion window will be restarted as soon as possible but will not be extended beyond the end of study day 10. Any study infusion interruptions will be recorded, including the reason for the interruption.

In the case of a significant safety concern related to the drug administration, the study drug should be discontinued until the situation is evaluated by the safety officer. Since there is no specific antidote for L-citrulline, in almost all cases simply discontinuing the study drug is appropriate. Breaking the blind will not generally provide increased safety. The study medication blind shall not be broken unless information concerning the study medication is clearly necessary for the medical treatment of the participant. The decision to unblind study personnel for an adverse event or other circumstance will be determined by the safety officer in consultation with the investigators. If unblinding occurs, the investigator will notify the IRB within 24 hours. The date, time, and reason that the blind was broken will be provided and documented in the CRF.

6.0 STUDY POPULATION AND ENROLLMENT

6.1 Participant Enrollment

Up to 66 participants will be enrolled. The study is expected to accrue over about 6-9 months. Participants will be recruited from the University of Arkansas for Medical Sciences Hospital. Additional

sites may be added at the discretion of the investigators and the sponsor. Participants who withdraw or prematurely discontinue study material infusion will be included in an intention to treat analysis. Safety data will continue to be collected up to hospital discharge for any participants who are withdrawn from the study.

6.2 Inclusion Criteria

Participant eligibility is determined based on the selection of criteria detailed below:

1. Age 18-65 years.
2. Clinical evidence of COVID-19 (SARS-CoV2) infection, defined as a positive COVID-19 laboratory test plus evidence of an acute hypoxic respiratory illness requiring oxygen.
3. Admitted and transferred to floor without intubation.

6.3 Exclusion Criteria:

Patients meeting any of the following criteria will not be eligible for participation in the study:

1. No consent/inability to obtain consent
2. Patient, surrogate, or physician not committed to full support
3. Malignant or other irreversible condition and estimated 28-day mortality $\geq 50\%$
4. Moribund patient not expected to survive 48 hours (as defined by primary medical team) from start of study infusion
5. End-stage Liver Disease as defined by Child-Pugh Score > 9
6. Currently enrolled in, or participated in another study of an investigational compound within the last 30 days
7. Pregnant female, or female who is breast feeding
8. Allergy to L-citrulline or arginine or any citrulline- or arginine-containing product
9. Patient not otherwise suitable for the study in the opinion of any of the investigators
10. Requirement for intubation and invasive mechanical ventilation before study enrollment

6.4 Informed Consent

Study personnel (either coordinator or investigators) will identify potential candidates for enrollment utilizing the inclusion and exclusion criteria per protocol. Once a potential participant is identified, the study coordinator or principal investigator will meet with the patient and/or legally authorized representative and will describe the proposed study protocol in lay terminology. Prior to performing any study procedures, an IRB-approved informed consent form (ICF) must be signed and dated by each study participant or legally authorized surrogate representative and the study investigator or person informing the subject and obtaining the consent. Prior to taking part in the study, the participant or his or her legal representative should receive a copy of the signed and dated ICF. This procedure will be noted in the medical record. ICF will include PK sample retention for any exploratory analysis of certain intermediates of special interest to support further understanding of the role of citrulline.

A special vulnerable population, specifically cognitively impaired adults, will be eligible for enrollment in this proposed study. Although not all enrolled participants will be cognitively impaired, many could be. In cases where the potential participant is cognitively impaired, surrogate consent will be obtained from the participant's legally authorized representative according to state law. In these cases, the

participant will be “re-consented” at the earliest opportunity and given the option of continuing or stopping their participation.

All revised informed consent forms must be reviewed in the same manner and signed by any active participants or their legal representatives. The date that the informed consent is obtained will be documented in both the source documents and the case report form (CRF).

A subject number will be assigned to each participant after the ICF is signed. Numbers will be unique 3-digit numbers, assigned in ascending order starting with 001.

6.5 Excluded Medications

As interactions between citrulline and other medications are not known, no specific medications will be excluded. Patients should not receive exogenous citrulline or arginine (either intravenously or enterally) while participating in this study. Additionally, patients enrolled in another study of an investigational medicine will be excluded from participating.

6.6 Concomitant Medications

All medications administered as part of standard supportive care for acute hypoxemic respiratory failure will be allowed, including antibiotics, replacement dosages of corticosteroids, catecholamines and other vasopressors, and insulin for glucose control.

6.7 Criteria for Discontinuation or Withdrawal

The primary reason for treatment discontinuation will be noted in the case report form using the following categories:

- a. Adverse Event: The participant has experienced an adverse event that the investigator believes requires early termination because continued participation imposes an unnecessary risk to the participant’s health.
- b. Major Protocol Deviation: the enrolled participant failed to meet protocol entry criteria or did not adhere to protocol requirements, excluding prolonged interruption of study drug.
- c. Voluntary Withdrawal: The participant or legally authorized representative wishes to withdraw from the study. The reason for withdrawal, if provided, will also be documented in the CRF.
- d. Other: This category includes participants withdrawn for occlusion of an IV or loss of IV access.

6.8 Procedures for Discontinuation or Withdrawal of a Participant

If a participant is withdrawn from treatment and/or the study because of a clinically significant serious adverse event (SAE), the investigator will evaluate the urgency of the event. For urgent situations, the investigator will proceed with immediate treatment of the SAE and the participant’s condition according

to standard of care. The IRB will be notified of any clinically significant, unexpected, related SAE leading to the participant's withdrawal from the study and/or required treatment.

The investigator may terminate participation of a subject for safety if he or she believes that continued participation in the study would put the participant's health at unacceptable risk. In addition, a participant or legally authorized representative may discontinue his or her participation without giving a reason at any time during the study.

7.0 STUDY PLAN

7.1 Definition of Study Procedures (see Appendix A: Schedule of Events)

7.1.1 Demographics, Medical History, and Medication History

Demographics will include the age, gender, ethnicity, and race as described by the participant or participant's legally authorized representative. A complete medical history will include a review of all major body systems. All concurrent medical conditions will be recorded. Medication history will include all medications taken or administered within 72 hours of study drug administration.

7.1.2 Vital Signs Excluding Hemodynamics

Vital signs will be collected and recorded on the CRFs. For this study, vital signs will include temperature, heart rate (pulse), and respiratory rate. Blood pressure will be considered a hemodynamic assessment in this study.

7.1.3 Hemodynamic Assessments

Blood pressure measurements will represent a major component of the hemodynamic assessments. Vasopressor dosages in critically ill patients will also form a significant component of these assessments. Vasopressor Dependency Index (VDI) will be used as the measure of hemodynamic assessment. VDI is a continuous variable calculated by dividing vasopressor index (summation of all pressors) by MAP. VDI will be calculated at baseline (immediately before start of the infusion), again 2 hours after completion of the bolus, and every 4 hours during the infusion. Any cases where the VDI increases by more than 20% from baseline will result in interruption of the study infusion and review by the safety officer in an expedited fashion.

7.1.3.1 Blood Pressure Measurements

Blood pressure measurements will be taken from an arterial catheter if available and sphygmomanometer if an arterial catheter is not available. If a participant has an arterial catheter in place, the MAP measured by both the arterial catheter and the sphygmomanometer will be documented in case the arterial line is discontinued and not replaced during the study.

7.1.4 Mortality, Hospital, and ICU Length of Stay Assessment

Participant survival will be assessed at hospital discharge. ICU length of stay will be the total number of days the participant spends in the ICU from time of enrollment to hospital discharge. Re-admissions to the ICU during the initial hospital stay will be added to the initial ICU length of stay to determine a total number of ICU days. Hospital length of stay will be calculated as the number of days from enrollment to

hospital discharge. Once the patient is discharged from the hospital (to any disposition including home, home with help, rehab, or another hospital) or dies, hospital days will cease. Subsequent re-admissions to the hospital or ICU after hospital discharge will not be added to the hospital or ICU lengths of stay, respectively.

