2.0 STUDY SUMMARY

Title: Prospective, Randomized, Double-Blind, Placebo-Controlled Phase II Trial of Intravenous L-Citrulline to Delay and Potentially Prevent the Need for Invasive Mechanical Ventilation for Acute Hypoxemic Respiratory Failure in Patients with COVID-19 (SARS-CoV2) Illness.

Objective: To evaluate safety and efficacy of a bolus loading dose and continuous intravenous infusion of L-Citrulline compared to placebo in patients hospitalized with COVID-19 infection (SARS-CoV-2).

Hypothesis: Intravenous L-citrulline administration will safely restore the homeostasis of nitric oxide synthase by increasing both plasma citrulline and arginine levels. We also reason that restoration of citrulline/arginine balance through citrulline administration will safely re-establish homeostasis of NOS, lower oxidative stress, and reduce inflammation, thereby delaying and potentially preventing the need for invasive mechanical ventilation in patients hospitalized with COVID-19 infection (SARS-CoV-2).

Study Design:	
Prospective, randomized, placebo-controlled, double-blind design.
 
 1. Enrollment: approximately 6-9 months 2. Plasma citrulline and arginine levels at day 4 will represent the primary biochemical variable. 3. Vasomotor stability, as measured using a vasopressor dependency index (VDI), through study day 10, will represent the primary safety variable. 4. The length of time from the initiation of the treatment to an intubation event for invasive mechanical ventilation measured in hours will represent the primary clinical outcome. 5. Patients will be followed until hospital discharge for mortality, ICU and hospital lengths of stay, and a requirement for invasive mechanical ventilation and non-invasive mechanical ventilation with high flow nasal cannula or BiPAP as additional clinical endpoints. A further comparison will be performed at D28 and D60 based on telephone follow up for those discharged earlier. 6. Patients will exit the study early (prior to 10 days) if they recover and no longer require oxygen therapy.

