10.6.1 Secondary Clinical Endpoints

All-cause, hospital mortality, defined by whether the patient was discharged from the hospital alive or deceased, will be analyzed via two statistical methods. The proportion of patients who have died by hospital discharge will be analyzed using a Chi-square analysis or Fisher's Exact Test, if needed. In addition, time to death will also be analyzed using a log-rank method of a Kaplan-Meier analysis. ICU length of stay (LOS) will be defined in days as the time from study enrollment to the day ICU discharge orders are written, regardless of when the patient physically leaves the ICU. Comparison will be made between the two groups for total ICU length of stay which will include any days of ICU re-admission prior to hospital discharge. Hospital length of stay will be defined as time from study enrollment to first hospital discharge. We will consider both ICU LOS and hospital LOS as count measure and has the potential to follow a skewed distribution. Initially, we will assess the distributional assumption. We will use a generalized linear model (GLM) to compare the expected ICU LOS and hospital LOS between the two treatment groups (placebo and intravenous citrulline). Specifically, we will use a negative binomial distribution and log-link to account for potential over-dispersion. We will report point estimates for the group mean difference along with a 95% confidence interval. Overall duration of mechanical ventilation will be modeled with zero-inflated Poisson or negative binomial method using consent and post-infusion start time for two separate analysis.

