### **Statistical Method for the Secondary Clinical Efficacy Endpoints**

#### ***All-cause Hospital Mortality***

All-cause, hospital mortality, defined by whether the patient was discharged from the hospital alive or deceased, will be analyzed via two statistical methods. The proportion of patients who have died by

hospital discharge will be analyzed using a Fisher's Exact Test. Additionally, time to death will also be analyzed using Kaplan-Meier estimates of the survival functions. A log-rank test will be used to compare time to death for the two treatment groups. The hazard ratio of IV Citrulline compared with placebo and its corresponding two-sided 95% confidence interval will be estimated using a Cox proportional hazards (PH) model with treatment groups as the independent variable.

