#### ***Length of Hospital Stay***

Hospital length of stay will be defined as time from study enrollment to first hospital discharge. We will follow the same analytical plan for the length of ICU stay outcome.

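### Transfer to another hospital counts as hospital discharge, so a patient moved while still acutely ill enters hospital mortality as discharged alive with truncated stays, and the SAP sets no later analysis to correct this

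*Protocol*

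**What the plan says.** Protocol 7.1.4 puts a move to another hospital on the same footing as going home; its rule for a participant who leaves reads "discharged from the hospital (to any disposition including home, home with help, rehab, or another hospital) or dies, hospital days will cease". The same section states that "Participant survival will be assessed at hospital discharge", counts ICU days only up to hospital discharge, and adds: "Subsequent re-admissions to the hospital or ICU after hospital discharge will not be added to the hospital or ICU lengths of stay, respectively".

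The endpoint definitions follow this. Protocol 10.6.1 reads "All-cause, hospital mortality, defined by whether the patient was discharged from the hospital alive or deceased", and the SAP (All-cause Hospital Mortality) repeats "defined by whether the patient was discharged from the hospital alive or deceased". The SAP (Length of Hospital Stay) reads "Hospital length of stay will be defined as time from study enrollment to first hospital discharge". The SAP's ICU stay includes ICU re-admissions only if they precede hospital discharge. None of these places excepts transfer between acute hospitals.

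On follow-up, item 5 of the Protocol 2.0 study design says "Patients will be followed until hospital discharge for mortality, ICU and hospital lengths of stay, and a requirement for invasive mechanical ventilation", and then promises a further comparison at Day 28 and Day 60 by telephone for patients who left earlier. Sections 5.1, 7.2.2 and 7.2.3 repeat the calls. Appendix A schedules hospital status, ICU status and adverse event review at both. The SAP (Missing Data) undertakes to stay in contact after discharge and to try to establish whether every randomized patient is alive. Its Study Design section, however, takes clinical outcomes only as far as discharge and does not mention the calls.

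**The concern.** Hospital mortality and length of stay are meant to reflect the course of the acute illness. Under these definitions a patient who leaves for another ICU, perhaps still ventilated, is indistinguishable from one who walked out recovered. If transfer while acutely ill depends on severity, and the drug changes severity, the misclassification can differ by arm. Even if it does not differ, it removes deaths from both arms and shrinks the absolute difference.

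The primary endpoint is touched by a different route. If nobody records what happens at the receiving hospital, a deteriorating patient's time to intubation stops at the transfer. Log-rank and Cox analyses assume that censored patients carry the same future risk as those still observed, and that may fail for such a patient.

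**Working it through.** **Step 1. What happens to a patient transferred while still acutely ill.**

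| Outcome | Governing text | Result |
|---|---|---|
| Hospital mortality (proportion) | Protocol 7.1.4, 10.6.1; SAP All-cause Hospital Mortality | Discharged alive; a later death does not change this |
| Hospital stay | Protocol 7.1.4, 10.6.1; SAP Length of Hospital Stay | Ends at transfer |
| ICU stay | Protocol 7.1.4; SAP Length of ICU Stay | Ends at transfer; later ICU days not added |
| Time to death | Protocol 10.6.1; SAP All-cause Hospital Mortality | No horizon or censoring date stated, so not settled |
| Time to intubation | SAP Missing Data; Protocol 7.2.2; Appendix A | Probably censored at transfer |

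The last row rests on the data schedule. Appendix A marks ventilation status to Day 11, and Protocol 7.2.2 extends ventilator settings to discharge. Neither goes further, and the Day 28 and Day 60 columns have no ventilation item. The SAP censors at the latest time assessed and does not mention transfer.

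**Step 2. Reproduce the plan's mortality power.** Inputs from Protocol 10.4 and SAP Sample Size: 50% against 17%, 60 patients 1:1 (n = 30 per arm), two-sided pooled z-test at 0.05, stated power 80%.

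With d = p1 − p2 and p̄ = (p1 + p2)/2:

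- SE0 = √(2·p̄(1 − p̄)/n)
- SE1 = √((p1(1 − p1) + p2(1 − p2))/n)
- power = Φ((d − 1.96·SE0)/SE1)

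Here p̄ = 0.335, SE0 = 0.1219 and SE1 = 0.1142. Power = Φ((0.330 − 0.2389)/0.1142) = Φ(0.798) = 78.8%, close to the stated 80%.

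**Step 3. Hide a share f of deaths equally in both arms.** The documents give no transfer share, so f is an assumption. Observed rates become 0.50(1 − f) and 0.17(1 − f).

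| f | Observed rates | d | SE0 | SE1 | Power |
|---|---|---|---|---|---|
| 0 | 50.0% vs 17.0% | 0.330 | 0.1219 | 0.1142 | 78.8% |
| 3% | 48.5% vs 16.5% | 0.320 | 0.1209 | 0.1136 | 76.8% |
| 5% | 47.5% vs 16.2% | 0.314 | 0.1203 | 0.1133 | 75.4% |
| 10% | 45.0% vs 15.3% | 0.297 | 0.1185 | 0.1121 | 71.8% |

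The SAP actually tests the proportion with Fisher's exact test. Enumerating all tables at 30 per arm gives 70.8%, 67.1% and 63.3% power for f = 0, 5% and 10%. The level is lower, but the loss is similar.

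**Step 4. Hide deaths in one arm only.** Each hidden death moves the observed difference by 1/30 = 3.3 points. A hidden placebo death understates benefit; a hidden citrulline death overstates it.

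**Step 5. Primary endpoint.** Freedman's form is power = Φ(√E·(1 − HR)/(1 + HR) − 1.96). With HR 0.46 and E = 60 events it gives 81.7%, matching the stated 81%; this requires an observed intubation in all 60 patients. Losing 5% of events (E = 57) gives 79.7% and 10% (E = 54) gives 77.6%. These figures reflect lost events only. Bias from informative censoring is a separate matter and cannot be sized from the documents.

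**Step 6. Stays.** Mean stay is understated by the transfer share times the mean days remaining. Neither is given, so no figure is offered.

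**The case against.** The rule is explicit, prespecified and the same in both arms of a double-blind trial, and the endpoint is openly named hospital mortality. The site is a university hospital that treats critically ill participants in its own ICU, and nothing in the documents says that sick patients are moved out. If both arms lose equal mean days, the difference in mean stay is unchanged. The 50% rate in the power statement refers to patients needing ICU care, whereas enrolment is of non-intubated floor patients on oxygen. Mortality is a secondary endpoint. All of this stands, and it limits how much weight the point can bear.

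Three stronger readings are tempting and are not supported:

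- *That any death or intubation after transfer is lost.* The Protocol schedules two calls and says they will further evaluate clinical outcomes, the SAP commits to seeking vital status, and time to death carries no discharge cut-off. A later death may well be known. What is missing is a specified analysis that uses it and, for intubation, an item that records it.
- *That a transferred patient is scored as a success on the primary endpoint.* The discharge sentence governs hospital days. The SAP's general rule censors such a patient.
- *That power collapses.* Hiding one, two or three deaths in placebo and none in citrulline gives about 70%, 61% and 51%, but that is a one-sided scenario with no basis in the documents.

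The calls do not remove the point. Hospital mortality and both stays remain fixed at discharge by definition, whatever is learned later.

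**Conclusion.** The point holds for the endpoint definitions. As written, a patient transferred while acutely ill enters the mortality proportion as discharged alive, with truncated hospital and ICU stays, and no Day 28 or Day 60 analysis in the SAP compensates. For time to intubation the probable result is censoring at transfer, which may be informative; this is inferred from the schedule and the general censoring rule, since no text addresses transfer.

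The size is modest and conditional. With 3% to 10% of deaths hidden equally in both arms, the planned z-test loses about 2 to 7 points of power (78.8% to 76.8% or 71.8%). An imbalance of a single hidden death moves the difference by 3.3 points in either direction. Both rest on an assumed share and on the plan's own mortality rates. The true share may be near zero, in which case the effect is negligible. The change is worth making because it is cheap and the calls already exist.

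**What to change.** 1. In Protocol 7.1.4 and 7.2.3 (with 10.6.1 to match) and in the SAP sections on hospital mortality, ICU stay and hospital stay, state that transfer to another acute-care hospital does not end hospital stay, ICU stay, or follow-up for death and intubation.
2. Add final discharge date, intubation with its date, and vital status to the Day 28 and Day 60 calls.
3. Specify in the SAP an all-cause mortality analysis at Day 28, and at Day 60, for all randomized patients. This captures deaths after transfer however discharge is defined.
4. Report transfers by arm. For time to intubation, add a sensitivity analysis that treats acute-care transfers with unknown outcome as events, shown beside censoring at transfer. Censoring alone would largely restate the existing rule and keep its weakness.

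The cost is wording in two documents and a few extra questions in calls already scheduled, with no new visit or patient. Some outcomes at receiving hospitals may be unobtainable, which is why item 4 is needed.
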